1.3 Purpose

The purpose of this study is to evaluate the safety and effectiveness of the AFRS in patients with lateral, lateral recess and/or central canal stenosis due to facet degeneration at a single level from L3 to S1 who require a lumbar decompression and facetectomy compared to an instrumented posterolateral fusion control group. Safety of the AFRS device will be evaluated by the incidence, severity and device or procedure relatedness of all adverse events over the 24 month assessment period as compared to the control group. Effectiveness of the AFRS will be based on the improvement in symptom-related questionnaire scores, function, and neurological status.

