The leg pain VAS scores for subjects in each treatment group will be summarized separately by the more symptomatic and less symptomatic legs of each subject, as measured at baseline. For inference, the relevant hypothesis is

$$H: \mu_t - \mu_c < 0$$

where μ_t and μ_c are the average VAS scores for the more symptomatic legs (or less symptomatic legs, as appropriate) in the treatment and control groups, respectively.

Oswestry Disability Index (ODI)

The ODI scores for subjects in each treatment group will be summarized at the 3-, 6-, 12-, and 24-month time points. For the 24-month time point, a statistical test will be conducted. The relevant hypothesis is

$$H: \mu_t - \mu_c < \delta$$

where μ_t and μ_c are the average ODI scores in the treatment and control groups, respectively.

[REDACTED]

[REDACTED]

Adverse Events

All Adverse Events (AEs) will be tabulated and summarized as counts and percentages by treatment group. AEs will also be cross-tabulated separately according to treatment group and:

- Severity (Mild, Moderate, Severe)
- Seriousness (Serious, Non-serious)
- Device-Relatedness (Related, Not Related)
- Surgery-Relatedness (Related, Not Related)

In addition, the occurrence of any Unanticipated Adverse Device Effects (UADE) will be listed. The classification of severity, relatedness, and anticipated nature of AEs will be made by the Clinical Events Committee (CEC).

Summaries will include counts, percentages, and 95% Bayesian credible intervals for the difference in proportions between treatment groups. An analysis of safety outcomes which combines all AFRS treated patients (randomized and non-randomized) compared to control patients will also be performed. The statistical method for dichotomous outcomes (e.g., device-relatedness, surgery-relatedness) will be the Bayesian version of a comparison of proportions, described below. The statistical method for trichotomous outcomes (e.g., Severity) will be the Bayesian version of a comparison of polytomous outcomes, described below.

Surgical Revisions, Reoperations, Removals, and Supplemental Fixation

The incidence of a composite of surgical revisions, reoperations, removals, and supplemental fixation at the index level for subjects in each treatment group will be summarized at the 3-, 6-, 12-, and 24-month time points. For the 24-month time point, a statistical test will be conducted. The relevant hypothesis is

$$H: p_t - p_c < 0$$

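### The adverse-event severity comparison has no level for patients without an event, so it cannot measure incidence; the unit of the other adverse-event comparisons is not stated in the visible text

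*Combined protocol and SAP*

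**What the plan says.** Section 1.3 sets the safety aim: "Safety of the AFRS device will be evaluated by the incidence, severity and device or procedure relatedness of all adverse events", compared with the control group over 24 months. Incidence is named alongside severity and relatedness.

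The Adverse Events paragraph of section 8.7 begins: "All Adverse Events (AEs) will be tabulated and summarized as counts and percentages by treatment group". It continues: "AEs will also be cross-tabulated separately according to treatment group and" four attributes, namely severity (mild, moderate, severe), seriousness, device-relatedness and surgery-relatedness, the last three with two levels each. Then: "Summaries will include counts, percentages, and 95% Bayesian credible intervals for the difference in proportions between treatment groups". The two-level outcomes are to be compared as proportions. For severity: "The statistical method for trichotomous outcomes (e.g., Severity) will be the Bayesian version of a comparison of polytomous outcomes, described below".

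The paragraph does not say what the proportions are proportions of, and it gives no rule for a patient with several AEs. The methods it points to belong to section 8.8, which the contents list but which is redacted from the public text.

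**The concern.** A three-level severity outcome has no place for a patient who had no AE. Whoever enters the comparison has already had an event after randomisation, so the comparison describes how severe the AEs were given that they occurred. It does not describe how many treated patients had a severe one. If AFRS raised AEs of every severity in the same proportion, the split would not move.

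For seriousness and relatedness the question is open. If those proportions are shares of events, they have the same weakness. In addition, several events from one patient would be treated as independent, and the credible intervals would be too narrow wherever events in the same patient tend to fall in the same category.

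**Working it through.** The documents give no AE rate, severity split or within-patient correlation, so there is no planned figure to reproduce. What follows is a reading of the text and then an illustration on assumed inputs.

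**What the text fixes.** The levels of a polytomous outcome must together account for everyone in the denominator. Mild, moderate and severe account for all events, or for all patients with an event. They do not account for all treated patients, who would need a fourth level. This follows from visible text and does not depend on section 8.8.

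**What the text leaves open.** Related versus not related can split events. It can also split patients into those with and without a related AE. The visible wording allows both.

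**Size if events are the unit.** From the documents: the minimum arms of 200 and 100 (section 3.1), and flat or diffuse priors for secondary analyses (section 8.7), taken here as Beta(1,1). Assumed: control mean m of 0.5, 1 or 2 AEs per patient, exactly double with AFRS, and 15% of AEs severe in both arms. The severe share of events is then 15% against 15% at every m. With Poisson counts, the per-patient risk of a severe AE is 1 − exp(−0.15m) in control and 1 − exp(−0.30m) with AFRS.

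| m | Severe share of events, each arm | Patients with a severe AE, control | AFRS | Difference |
|---|---|---|---|---|
| 0.5 | 15% | 7.2% | 13.9% | 6.7 points |
| 1 | 15% | 13.9% | 25.9% | 12.0 points |
| 2 | 15% | 25.9% | 45.1% | 19.2 points |

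With negative binomial counts (dispersion 1) the differences are 6.1, 10.0 and 14.4 points.

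**Size if patients with an event are the unit.** At m = 1, 63.2% of control and 86.5% of AFRS patients have any AE. Grading each patient by worst event, the severe proportion is 13.9/63.2 = 22.0% against 25.9/86.5 = 29.9%. That is a difference of 7.9 points in place of 12.0: reduced, but not removed. It disappears only if the number of patients at each worst grade rises in the same proportion.

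**A two-level example.** Suppose 200 AFRS patients have 400 AEs, 40 of them device-related, and 100 controls have 100 AEs, 10 of them related. By event, the posterior means are 41/402 = 10.2% and 11/102 = 10.8%, a difference of −0.6 points (95% credible interval −7.8 to +5.5). By patient, if every related AE is in a different patient, they are 41/202 = 20.3% and 11/102 = 10.8%, a difference of +9.5 points (1.1 to 17.4). The posterior probability that AFRS is worse is then 98.6%.

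**Interval width.** In 1,500 simulated trials per setting (control means 1 and 2, doubled with AFRS; category shares 15% and 35%; Poisson and negative binomial counts), the true difference in event share is zero. Coverage is therefore how often the event-level interval contains zero. A separate run assumed a mean of 2.5 AEs per patient and 20% related.

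| Within-patient correlation | Coverage, doubling simulation | Coverage, separate run |
|---|---|---|
| 0 | 94–96% | not used |
| 0.1 | 90–93% | 89–91% |
| 0.3 | 78–91% | 77–82% |
| 0.5 | 70–87% | not used |

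**What a per-patient analysis would show.** For severe AEs, Poisson counts and no correlation, the per-patient interval excludes zero on the side of harm in 68% of trials at m = 1 and 91% at m = 2. A normal-theory power calculation gives 67% for the first. Across all severe-AE settings run, the range is 24% to 91%.

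**The case against.** The best reply is that section 8.8 is withheld and may define the unit and the handling of repeat events, so nothing can be called missing from the plan. The same named comparison of proportions is used elsewhere in section 8.7 for proportions of subjects, for example return to normal activities and rehabilitation use. Section 8.1 describes the pooled safety presentation in terms of patients. The AE paragraph sets no hypothesis or threshold, and section 8.7 calls secondary objectives after the first five explanatory and supportive.

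Most of this stands. A reader might infer that every AE comparison uses shares of events; for the two-level outcomes the documents do not say so. A reader might also infer that a doubling of AEs would go unseen. It would not: AE counts by arm are tabulated, and 400 events in 200 patients against 100 in 100 is plain once the 2:1 allocation is allowed for. Index-level surgery is compared per subject, and a serious device-related AE makes the patient a failure on the primary endpoint.

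Two things remain. The three-level severity outcome is in the visible text and cannot contain patients without an AE. And none of the other safeguards is an inferential comparison of the per-patient incidence of AEs overall, severe AEs, or non-serious related AEs.

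**Conclusion.** The severity comparison as written conditions on having had an AE and does not measure incidence. With events as the unit, a proportional rise at every severity shows as no difference, while under the assumed rates the per-patient excess of severe AEs is about 6 to 19 points for a doubling. If patients with an event are the unit, the excess may be only reduced.

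For seriousness and relatedness the finding is conditional: the unit is not stated where it can be read. A general statement that the 95% intervals are too narrow is not supported. It needs both events as the unit and correlation within patients, and the documents give neither; at zero correlation coverage is nominal. All rates, splits and correlations above are assumptions. This is an improvement that costs nothing in data or patients. It does not threaten the primary conclusion.

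**What to change.** In the Adverse Events paragraph of section 8.7:

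- Make the patient the unit for every AE comparison, with all patients in the analysis set as denominator.
- Count each patient once for any AE, any serious AE, any device-related AE and any surgery-related AE.
- Compare severity by each patient's worst grade, with no AE as the lowest level. Reconcile the three-level list with the four grades in section 6.1.4, which include life-threatening.
- Keep event counts as description only.
- Apply the same rule to the comparison that pools randomised and training AFRS patients.

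If section 8.8 already fixes the unit this way, a cross-reference and the corrected severity levels are enough. The cost is SAP wording and table shells; the data are already to be collected.

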8.3 Randomization, Sample Size, and Analysis Plan

This study is designed to adaptively determine the proper sample size. Possible sample sizes are 300, 450, 600, and 750 (maximum). Randomization will follow a 2:1 (treatment:control) allocation ratio and be stratified by site, using a blocked randomization scheme with blocks of randomly varying sizes. Further details on the randomization process are provided in **Section 5.2**.

In addition to the planned interim analyses that will determine the sample size, there will be several interim analyses conducted for the purpose of possibly declaring an early win. The first of these will occur when 300 subjects have completed 2 years of follow-up. If the trial does not stop for success at that analysis, a second analysis will occur when 450 have completed 2 years of follow-up. If the trial does not stop for success at that analysis, a final analysis will occur when the entire enrolled cohort has completed 2 years. It is not necessary for the trial to have stopped enrollment in order for the interim “Early Win” analyses to occur. For example, the first Early Win analysis (when 300 have completed 2 years) will occur even if the trial is still enrolling (i.e., the sample size determination algorithm has not determined the final sample size). Of course, if the final sample size is 300, there can be only 1 Win analysis (when the full cohort has reached 2 years); if the final sample size is 450, there can be only 2 Win analyses (when 300 have reached 2 years and when the full cohort has reached 2 years).

The sample size determination analyses and the “Early Win” interim analyses are triggered by different circumstances (number enrolled versus number completing 2 years) and are expected to follow different analysis schedules (i.e., although it is possible, a sample size analysis and an early win analysis are unlikely to occur simultaneously).

Further details on this analysis plan are given below.

Determination of Non-Inferiority and Superiority (“Win” Analyses)

Interim “Win” analyses are scheduled to occur when 300 and 450 subjects have completed 2 years of follow-up. A final analysis will occur when the entire enrolled cohort has completed 2 years of follow-up. At each of these analyses, the probability of non-inferiority $\Pr(H_{\delta=0.15} | \text{data})$ will be calculated, based on all observed data, including predicted 2-year outcomes for those subjects who have not reached 2 years.

[REDACTED]

[REDACTED]

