8.7 Secondary Objectives

General Considerations for Secondary Objectives

While there are many pre-specified secondary objectives, only the first five are designated as objectives for which FDA-approved labeling claims may be sought, and only for the results measured at the 24-month time point. The rest of the secondary objectives have been pre-specified but are intended to be explanatory and supportive in nature, and not the basis of specific labeling claims.

As indicated in “Analysis Methods for Secondary Objectives,” below, flat or diffuse prior distributions have been identified for all secondary objective analyses. For any hypothesis test, a posterior probability greater than 95% for any hypothesis will be considered to constitute evidence in favor of the hypothesis, in the same sense that a frequentist analysis would reject a null hypothesis when $p < 0.05$ and call it “statistically significant.” However, for the subset of secondary objectives on which labeling claims may be sought, the posterior probability threshold for making the claim is somewhat more stringent. See the section entitled “Multiplicity Considerations,” below.

Zurich Claudication Questionnaire (ZCQ) – Physical Function Domain (PF)

The ZCQ PF domain scores for subjects in each treatment group will be summarized at the 3-, 6-, 12-, and 24-month time points. For the 24-month time point, a statistical test will be conducted. The relevant hypothesis is

$$H: \mu_t - \mu_c < \delta$$

where μ_t and μ_c are the average PF scores in the treatment and control groups, respectively, and δ is the margin of non-inferiority.

[REDACTED]

[REDACTED]

Zurich Claudication Questionnaire (ZCQ) – Symptom Severity Domain (SS)

The ZCQ SS domain scores for subjects in each treatment group will be summarized at the 3-, 6-, 12-, and 24-month time points. For the 24-month time point, a statistical test will be conducted. The relevant hypothesis is

$$H: \mu_t - \mu_c < \delta,$$

where μ_t and μ_c are the average SS scores in the treatment and control groups, respectively, and δ is the margin of non-inferiority.

[REDACTED]

[REDACTED]

Back Pain on Visual Analog Scale (VAS)

The back pain VAS scores for subjects in each treatment group will be summarized at the 3-, 6-, 12-, and 24-month time points. For inference, the relevant hypothesis is

$$H: \mu_t - \mu_c < 0,$$

where μ_t and μ_c are the average back pain VAS scores for subjects in the treatment and control groups, respectively. [REDACTED]

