Narcotic Medication Usage

The proportions of subjects in each treatment group who are not on narcotic pain relieving medications and in whom an epidural injection, denervation procedure or other procedure for pain management has not been performed at the index level will be summarized at the 3-, 6-, 12-, and 24-month time points. For the 24-month time point, a statistical test will be conducted. The relevant hypothesis is

$$H: p_t - p_c > 0,$$

where p_t and p_c are the proportions of subjects in the treatment and control groups, respectively, who are not taking narcotic medications and have not had pain management procedures at the index level. [REDACTED]

[REDACTED]

Length of Hospital Stay

The length of hospital stay will be calculated for each subject (with the day of surgery = Day 0) and summarized by treatment group. A statistical test of the difference in length of stay between treatment groups will be conducted. The relevant hypothesis is

$$H: \mu_t - \mu_c < 0$$

where μ_t and μ_c are the average stays in the treatment and control groups, respectively. It is anticipated that the distribution of hospital stays will be somewhat skewed, so the data will be ranked and the statistical method will be the Bayesian version of the Wilcoxon Rank-Sum test, described below. If a subject should die in hospital before being discharged, that subject will be assigned a length of stay that is 1 day greater than the maximum observed length of stay for any patient.

Duration of Procedure

The duration of the procedure will be summarized for the treatment and control groups. Statistical summaries will include means, medians, and standards of deviation, as well as 95% credible intervals for μ_t , μ_c , and $(\mu_t - \mu_c)$. A statistical test will be conducted on the hypothesis

$$H: \mu_t - \mu_c < 0$$

where μ_t and μ_c are the average procedure durations in the treatment and control groups, respectively. The statistical method will be the Bayesian version of a t-test, described below.

Instrumentation Time

The portion of the procedure time that is due to Instrumentation Time will be summarized for the treatment and control groups. Statistical summaries will include means, medians, and standards of deviation, as well as 95% credible intervals for μ_t , μ_c , and $(\mu_t - \mu_c)$. A statistical test will be conducted on the hypothesis

$$H: \mu_t - \mu_c < 0,$$

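### The length-of-stay hypothesis concerns average stay but is tested on ranks alone, so a rank result could be reported as a shorter average when the averages are equal

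*Combined protocol and SAP*

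**What the plan says.** All the relevant text is in section 8.7.

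- **Hypothesis.** Under Length of Hospital Stay, H is mu_t - mu_c < 0, and the two parameters "are the average stays in the treatment and control groups, respectively".
- **Method.** The next sentence gives the reason for ranking, "It is anticipated that the distribution of hospital stays will be somewhat skewed", and then the method: "so the data will be ranked and the statistical method will be the Bayesian version of the Wilcoxon Rank-Sum test, described below".
- **In-hospital death.** If a patient dies before discharge, "that subject will be assigned a length of stay that is 1 day greater than the maximum observed length of stay for any patient".
- **Decision rule.** The general considerations at the start of 8.7 say that "a posterior probability greater than 95% for any hypothesis will be considered to constitute evidence in favor of the hypothesis". They also say that "flat or diffuse prior distributions have been identified for all secondary objective analyses".
- **Status.** Only the first five secondary objectives may support labelling claims. Length of stay comes well after the fifth, so it is supportive.
- **Neighbouring endpoints.** Procedure duration, instrumentation time and blood loss also have hypotheses about means. They get a Bayesian t-test and 95% credible intervals for each mean and for the difference. Length of stay gets an unspecified summary by arm and the rank test.

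The rank-sum method itself would be in section 8.8, which the table of contents lists and the public copy redacts. The redaction is not a fault in the plan.

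**The concern.** The hypothesis and the test address different quantities. A rank-sum analysis compares how often a random AFRS patient leaves earlier than a random control patient. Once the days are ranked, a 14-day stay and a 30-day stay at the top of the list carry the same information. An average depends on exactly that information.

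Suppose many AFRS patients go home a little earlier while a few stay much longer. The rank comparison can then favour the AFRS although the averages are equal, or even when the AFRS average is longer. Under the 95% rule the report would say that average stay is shorter. No interval for the mean difference is promised that would show otherwise.

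At stake is the accuracy of one supportive statement. The primary non-inferiority decision, the sample size and the labelling claims do not depend on it.

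**Working it through.** **Figure to reproduce.** None. The plan gives no power, effect size or distribution for length of stay.

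**Inputs from the documents.** Posterior threshold 0.95, flat or diffuse priors (8.7). Allocation 2:1, total sample size 300 to 750 (8.3), so 200:100 up to 500:250.

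**Assumed inputs.** Control stays of 1, 2, 3, 4, 5, 6 and 8 days with probabilities 0.10, 0.20, 0.30, 0.20, 0.12, 0.05 and 0.03. The mean is 0.10 + 0.40 + 0.90 + 0.80 + 0.60 + 0.30 + 0.24 = 3.34 days. For the AFRS, a share q of patients moves from 3 days to 2, and a share e moves from 3 days to a long stay of L days. Setting e = q/(L - 3) keeps the mean at 3.34.

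**Step 1: the quantity a rank test responds to.** Let theta = Pr(AFRS shorter) + 0.5 Pr(tie). A patient staying x days scores g(x) = Pr(C > x) + 0.5 Pr(C = x) against control:

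- g(2) = 0.70 + 0.10 = 0.80
- g(3) = 0.40 + 0.15 = 0.55
- g(10) = g(14) = 0

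Therefore theta = 0.5 + q(0.80 - 0.55) - 0.55e.

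- q = 0.10, L = 14: e = 0.10/11 = 0.0091; theta = 0.5 + 0.025 - 0.005 = 0.520
- q = 0.20, L = 10: e = 0.20/7 = 0.0286; theta = 0.5 + 0.050 - 0.016 = 0.534
- q = 0.20, L = 14: e = 0.20/11 = 0.0182; theta = 0.5 + 0.050 - 0.010 = 0.540

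The means are equal, yet theta exceeds 0.5.

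**Step 2: approximate firing rate.** The standard error of the estimated theta is about sqrt[(n + m + 1)/(12nm)], times sqrt(1 - sum of cubed pooled probabilities) for ties. For q = 0.10:

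- 200:100: sqrt(301/240,000) = 0.0354; the tie factor sqrt(0.958) gives 0.0347; z = 0.020/0.0347 = 0.58; Phi(0.58 - 1.645) = 14%
- 500:250: sqrt(751/1,500,000) = 0.0224, with ties 0.0219; z = 0.91; Phi(0.91 - 1.645) = 23%

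**Step 3: simulation, 4,000 trials per cell.** The rank rule is approximated by a flat-prior posterior on the difference in mean ranks, declared above 0.95. The comparator is a flat-prior t-type test on days. Lognormal rows have mean 3.5 days in both arms.

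| Scenario | Rank rule, 200:100 | Rank rule, 500:250 | Test of means, range over sizes run |
|---|---|---|---|
| Identical shapes | 4.8% | 5.5% | 4.6-5.4% |
| q = 0.10, AFRS tail at 14 days | 15.1% | 24.2% | 4.4-5.5% |
| q = 0.20, AFRS tail at 10 days | 27.3% | 50.0% | 4.9-5.3% |
| q = 0.20, AFRS tail at 14 days | 34.1% | 59.3% | 5.0-5.8% |
| Lognormal, log-SD 0.5 AFRS, 0.4 control | 20.1% | 37.0% | 4.9-5.4% |
| Lognormal, log-SD 0.6 AFRS, 0.4 control | 51.5% | 84.9% | 5.0-5.5% |
| q = 0.20, tail at 14 days in control instead | 0.2% | 0.1% | 3.4-4.2% |
| AFRS mean truly 0.22 day longer | 21.7% | 41.0% | 0.2-0.5% |

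An asymptotic Wilcoxon-Mann-Whitney test agreed with the rank rule within about 3 points in the discrete rows, and with step 2 (14.3% and 23.4% for q = 0.10).

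**Other assumed shapes.** Lognormal with log-SD 0.6 (AFRS) against 0.5 (control) gave about 18% and 34%. Long-stay tails in 10% of AFRS and 5% of control patients gave 16% and 29% in one simulation, and 18% and 27% in another.

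In the rows where the AFRS has the tail or the wider spread, the rate rises with sample size because theta is truly above 0.5.

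**The case against.** Much of the case on the other side stands.

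- **Ranking is defensible.** A reader might infer that the rank test is the wrong test, or that it is valid only when the arms differ by a pure shift. Neither follows. If one arm's stays are stochastically shorter, the mean and theta agree in direction. That includes proportional changes, such as lognormal stays with equal log-SD. Disagreement needs crossing distributions.
- **The high rates are partly power.** With theta above 0.5, AFRS patients really do tend to leave earlier. The result is an error only when worded as a statement about the average, which is how H is worded.
- **The asymmetry is assumed.** The operations share an approach and a decompression (3.2.2) and discharge criteria (5.4). Section 9.1 expects procedural risks like those of other posterior fixation, and 8.7 expects only some skew. Nothing in the documents says the AFRS will have the longer tail. If control has it, the rule almost never fires.
- **The method text is hidden.** Section 8.8 might define the posterior on a rank parameter. That would not remove the mismatch, because H and the ranking step are both visible in 8.7, and ranks alone cannot recover a difference in mean days.
- **The death rule is coherent.** A reader might call it a flaw because a death becomes one day more than the longest stay. As a worst-rank score it does its job. It would be unsuitable only inside an average of days.
- **Reimbursement.** Section 3.1 mentions outcome measures to support reimbursement but does not name length of stay, so no stake is inferred from it.

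**Conclusion.** The mismatch between hypothesis and test is real and is visible within one paragraph of 8.7. Its consequence is conditional. With equal true means and an AFRS distribution that is moderately wider or heavier-tailed, the rule would report a shorter average stay in roughly 15% to 35% of trials, and more often with larger shape differences. The rate is about 5% when shapes are identical, and 0.2% or less in the case run with the tail in control. These figures rest on assumed distributions and an approximated rank-sum model.

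A reader might infer that the plan's error rate for this endpoint is generally inflated. The documents do not support that: the rule is calibrated for its own rank null, and no stay distribution is given. Importance is low, because the endpoint is supportive, lies outside the five objectives eligible for labelling claims, and does not touch the primary decision.

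**What to change.** 1. Keep the rank test and the maximum-plus-one-day death score, and describe the latter as a worst-rank score.
2. Restate H as Pr(AFRS stay shorter) + 0.5 Pr(tie) > 0.5.
3. Add the difference in mean days with a 95% credible interval, as already promised for procedure duration, instrumentation time and blood loss. Use a method that allows skew and unequal variances, for example a Bayesian bootstrap.
4. Compute that difference in the ITT population from actual days in hospital, using days to death for a patient who dies there. List in-hospital deaths by arm, since an early death would otherwise look like a short stay. Show the result without deaths as a sensitivity analysis only, because restricting to patients discharged alive conditions on a post-randomization outcome.
5. Base any statement about average stay on that interval, not on the rank test.

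The cost is a few lines of SAP text and one interval. Data collection and sample size do not change. The small downside is that a rank-based win can no longer be reported as a shorter average stay.
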